### **11.2 Withdrawal of Subjects from the Study**

A subject may be withdrawn from the study at any time if the subject, the investigator, or the Sponsor feels that it is not in the subject's best interest to continue.

All subjects are free to withdraw from participation at any time, for any reason, specified or unspecified, and without prejudice.

Reasonable attempts will be made by the investigator to provide a reason for subject withdrawals. The reason for the subject's withdrawal from the study will be specified in the subject's source documents. As noted above, subjects who discontinue study treatment early (i.e., they withdraw prior to Visit 2) should have an early discontinuation visit. Refer to 9.4 for early termination procedures.

### 11.3 Replacement of Subjects

Subjects who withdraw from the study treatment will not be replaced.

Subjects who withdraw from the study will not be replaced.

## 12 PROTOCOL VIOLATIONS

A protocol violation occurs when the subject, investigator, or Sponsor fails to adhere to significant protocol requirements affecting the inclusion, exclusion, subject safety and primary endpoint criteria. Protocol violations for this study include, but are not limited to, the following:

- Failure to meet inclusion/exclusion criteria
- Use of a prohibited concomitant medication
- Non-compliance with study drug regimen

Failure to comply with Good Clinical Practice (GCP) guidelines will also result in a protocol violation. The Sponsor will determine if a protocol violation will result in withdrawal of a subject.

When a protocol violation occurs, it will be discussed with the investigator and a Protocol Violation Form detailing the violation will be generated. This form will be signed by a Sponsor representative and the Investigator. A copy of the form will be filed in the site's regulatory binder and in the Sponsor's files.

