### 7.2 Blinding

Neither subjects nor investigators will be blinded.

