## **11 DISCONTINUATION AND REPLACEMENT OF SUBJECTS**

### **11.1 Early Discontinuation of Study Drug**

A subject may be discontinued from study treatment at any time if the subject, the investigator, or the Sponsor feels that it is not in the subject's best interest to continue. The following is a list of possible reasons for study treatment discontinuation:

- Subject withdrawal of consent (or assent)
- Subject is not compliant with study procedures
- Adverse event that in the opinion of the investigator would be in the best interest of the subject to discontinue study treatment
- Protocol violation requiring discontinuation of study treatment
- Lost to follow-up
- Sponsor request for early termination of study

If a subject is withdrawn from treatment due to an adverse event, the subject will be followed and treated by the Investigator until the abnormal parameter or symptom has resolved or stabilized.

All subjects who discontinue study treatment should come in for an early discontinuation visit as soon as possible and then should be encouraged to complete all remaining scheduled visits and procedures.

All subjects are free to withdraw from participation at any time, for any reason, specified or unspecified, and without prejudice.

Reasonable attempts will be made by the investigator to provide a reason for subject withdrawals. The reason for the subject's withdrawal from the study will be specified in the subject's source documents Refer to Section 9.4 for early termination procedures.

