5.1 Populations

Intention-to-treat (ITT)

All randomized study subjects. This will be seen as the primary population for the analysis.

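### Protocol 11.1, 11.2 and 12 do not separate stopping ointment from leaving the study, so a discretionary withdrawal before Visit 2 can remove a randomised patient from the SAP's all-randomised primary analysis

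*Protocol*

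**What the plan says.** **Violations.** Protocol section 12 lists failure to meet the eligibility criteria, "Use of a prohibited concomitant medication" and "Non-compliance with study drug regimen" among the violations. On the consequence it says only: "The Sponsor will determine if a protocol violation will result in withdrawal of a subject". Each violation is discussed with the investigator, who signs the form together with the Sponsor. Section 6 names oral and intravenous antibiotics as the prohibited drugs.

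**Stopping treatment.** Section 11.1 lists non-compliance and violations among the reasons for stopping study treatment. It has these patients attend an early discontinuation visit, and says they "then should be encouraged to complete all remaining scheduled visits and procedures".

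**Leaving the study.** Section 11.2 allows the patient, the investigator or the Sponsor to end participation whenever one of them judges that staying in does not serve the patient. It then refers back to 11.1 but describes the patients differently: "subjects who discontinue study treatment early (i.e., they withdraw prior to Visit 2) should have an early discontinuation visit".

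**Masking.** Section 7.2: "Neither subjects nor investigators will be blinded".

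**Outcome and analysis.** Infection is determined at Visit 2 (section 9.2, item 4). The early withdrawal visit (section 9.4) covers adverse events, medication changes and an eye examination, with no infection determination. SAP 5.1 defines the intention-to-treat set as: "All randomized study subjects. This will be seen as the primary population for the analysis". SAP section 7 leaves anyone without a primary outcome out of the primary analysis, does not impute, and shows the reason in the flow diagram.

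**The concern.** An all-randomised analysis protects the comparison only if outcomes are sought for all randomised patients whatever happens to their treatment. Here the protocol can itself create a missing outcome. Someone decides after randomisation, without stated criteria, that a patient is withdrawn; no infection determination is then planned; and the SAP drops the patient. Ordinary loss to follow-up is different, because the trial does not choose it.

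Two features make this more than untidy wording. Nothing in the documents keeps knowledge of the arm away from the decision. And one class of violation, oral or intravenous antibiotic use, may be a response to a suspected wound infection, so the patients at risk of removal could be the ones who carry the endpoint. With few infections expected, a handful of such removals, uneven between arms, could change the result.

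**Working it through.** **1. How a violation can lead to a lost outcome**

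- *Known before Visit 2, withdrawn from the study:* no Visit 2; section 9.4 records no infection status; SAP section 7 excludes the patient. The outcome is lost.
- *Known before Visit 2, ointment stopped only (11.1):* the patient is encouraged to attend Visit 2. The outcome is usually kept.
- *Found at Visit 2:* infection status is determined at that visit. Later withdrawal does not erase it, and under SAP 5.1 and 7 the patient stays in.

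Sections 11.2 and 12 do not say which of the first two routes applies.

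**2. Which violations are known early**

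- *Non-compliance:* measured by a diary and returned tubes brought to study visits (section 7.7) and reviewed at Visit 2, item 1. No earlier post-operative check is scheduled, so most of it surfaces when infection is recorded.
- *Antibiotic use:* medication is also reviewed at Visit 2, so use first learned of there costs nothing. Use that comes to light earlier is exposed.
- *Ineligibility after randomisation:* randomisation is at the pre-operative visit (sections 8 and 9.1), but section 5.3 excludes oral or intravenous antibiotics in the 10 days before surgery and intravenous antibiotics during it. Either can arise after randomisation and be known well before Visit 2.

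**3. The plan's power figure**

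Inputs from SAP 2.1 and 6.1: 200 per arm, 0.2% v 5%, Fisher's exact test; the 95% confidence level is read as two-sided 0.05. Power is the sum, over all pairs (i, j) with Fisher p ≤ 0.05, of Bin(i; 200, 0.002) × Bin(j; 200, 0.05). Result: 87.1%, against the stated 87%. The figure reproduces, and it needs an outcome from all 400.

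With equal, non-selective loss (rates assumed):

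- 5% lost, 190 per arm: 84.4%
- 10% lost, 180 per arm: 81.2%

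**4. Selective loss, as an illustration**

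At the SAP's planning rates the infections number 200 × 0.002 = 0.4 on antibiotic and 200 × 0.05 = 10 on control. Take 1 and 10 as assumed counts and remove infected controls (two-sided Fisher p):

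- none removed, 1/200 v 10/200: p = 0.011
- three removed, 1/200 v 7/197: p = 0.036
- four removed, 1/200 v 6/196: p = 0.066

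With no infections on antibiotic, 6 v 0 at 200 per arm gives p = 0.030 and 5 v 0 gives p = 0.061.

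**5. Non-selective loss of infections**

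If 5% to 10% of controls (10 to 20 of 200, assumed) were lost for reasons unrelated to infection, the expected infections lost at 5% would be 10 × 0.05 = 0.5 to 20 × 0.05 = 1.0. A large effect therefore requires removal that is related to infection.

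**The case against.** The case on the other side is substantial.

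- **Who holds the power.** A reader might infer that the unmasked investigator can also remove patients from the study for non-compliance. Section 12 gives the violation decision to the Sponsor alone. The investigator's power in 11.2 rests on best interest, and non-compliance in 11.1 is a reason to stop treatment. This stands. The Sponsor's masking is not stated either way, though the form is agreed with an unmasked investigator and the Sponsor is also the recruiting institution.
- **Timing.** A reader might take every non-compliant patient as exposed; at an assumed 5% to 10% that would be 20 to 40 of 400. The documents do not support this count, because compliance and infection are reviewed at the same visit. This also stands.
- **Wording.** The sentence in 11.2 points back to 11.1 and orders only the visit that 11.1 already requires, and 11.3 lists leaving treatment and leaving the study separately. That shows the protocol knows the distinction. It does not settle what section 12 means, and the parenthesis in 11.2 still runs against 11.1.
- **Disclosure.** Withdrawal reasons, signed violation forms and the flow diagram are all planned. They would make exclusions visible but would not recover the outcomes.
- **Event numbers.** The 5% behind the ten control infections is what the SAP calls a maximum acceptable rate, not an expected one. The p-values show that the test is fragile with rare events; they do not measure how many outcomes would be lost.

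**Conclusion.** The inconsistency is real and worth correcting. Sections 11.1, 11.2 and 12 leave open whether a violation or a treatment stop ends study participation. Where it does so before Visit 2, the outcome is lost and the patient leaves the primary analysis. In an open-label trial this lets a discretionary post-randomisation decision undermine the all-randomised population, possibly in relation to infection when the violation is antibiotic use.

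The size cannot be derived from the documents. It is probably confined to violations known before Visit 2. The loss rates and infection counts in the calculations are assumptions, and the shift from p = 0.011 to p = 0.066 needs four infected controls, and no others, to be removed.

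A reader might go further and conclude that the intention-to-treat analysis is defeated. The documents do not support that: the SAP still defines the set as everyone randomised, a withdrawn patient with a recorded outcome stays in, and 11.1 leans towards keeping patients in follow-up.

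**What to change.** 1. Reconcile sections 11.1, 11.2 and 12 so that discontinuing study treatment and leaving the study are distinct, and say in section 12 which of the two is meant.
2. State that a protocol violation or non-compliance is not by itself a reason to end outcome follow-up to Visit 2. Leave the consent-withdrawal and best-interest provisions, and any rule on stopping ointment, as they are.
3. Delete the parenthesis in 11.2 that describes early treatment stop as withdrawal before Visit 2.
4. Add infection status, by the section 4.1 criteria, to the early withdrawal visit in section 9.4.
5. In the flow diagram, report by arm and separately: stopped ointment but still followed; and withdrawn from follow-up, with who decided and why.

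The SAP describes randomisation and outcome assessment in the past tense. If follow-up is already complete, item 5 can still be done, together with a sensitivity analysis for missing outcomes.

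The cost is protocol wording and one extra item at a visit that already includes an eye examination. The small downside is that more non-adherent patients stay in the primary analysis, which is what the stated population requires.

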## 13 STATISTICAL METHODS AND CONSIDERATIONS

Prior to the analysis of the final study data, a detailed Statistical Analysis Plan (SAP) will be written describing all analyses that will be performed. The SAP will contain any modifications to the analysis plan described below.

### 13.1 Data Sets Analyzed

All randomized subjects who have completed one week of study drug or placebo will be included in data analysis.

All eligible patients who are randomized into the study and receive at least one dose of the study drug (the Safety Population) will be included in the safety analysis.

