## 3 STUDY DESIGN

### 3.1 Study Overview

This is a single center, placebo-controlled, randomized trial. 400 subjects are planned. Subjects will be randomly assigned to a study drug or to a placebo. Each subject will apply a single dose of topical study drug or placebo four times daily to their surgical wounds over the course of one week.

Screening data will be reviewed to determine subject eligibility. Subjects who meet all inclusion criteria and none of the exclusion criteria will be entered into the study.

The following treatment regimens will be used:

- Experimental treatment: topical ophthalmic antibiotic ointment (e.g. erythromycin, bacitracin or polybac)
- Placebo: artificial tear ointment (e.g. Refresh PM)

Total duration of subject participation will be from the time of approval for eyelid surgery to post-operative visit #1 (either one or two weeks after surgery). Total duration of the study is expected to be 2 years.

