## 4.2 Secondary Efficacy Endpoints

- The rate of superficial and deep SSI in high infection-risk groups such as patients with diabetes, those who smoke, those on chronic high-dose steroids, etc.
- The classification of types of complications (e.g. allergic dermatitis) related to antibiotic ointment and artificial tear ointment use as well as their respective rates.

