### 7.4.2 Dispensing

Study drug or placebo will be dispensed by an outpatient pharmacist.

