## 7.7 Measures of Treatment Compliance

Subjects will be asked to keep a patient diary noting the day and date they take their study drug and any adverse events. They will be asked to bring their patient diary to each study visit along with all used and unused study drug containers.

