### 13.4 Analysis of Secondary Endpoints

T-test or a linear regression model (with no covariates other than study arm).

Adverse events will be tabulated by treatment group and will include the number of patients for whom the event occurred, the rate of occurrence, and the severity and relationship to study drug.

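### Protocol 13.1 limits the Safety Population to eligible patients, although exclusion criteria can be met after randomization, and the SAP does not say which population applies to adverse events

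*Protocol*

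**What the plan says.** Protocol 13.1 describes two data sets. The first is for the general analysis: "All randomized subjects who have completed one week of study drug or placebo will be included in data analysis". The second is the safety set: "All eligible patients who are randomized into the study and receive at least one dose of the study drug (the Safety Population". The second adds an eligibility condition that the first lacks, and it names only the study drug where the first names drug or placebo.

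Protocol 13.4 states the safety output: "Adverse events will be tabulated by treatment group". Protocol 4.2 makes complications of both products an endpoint: "related to antibiotic ointment and artificial tear ointment use as well as their respective rates".

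Protocol 12 foresees that ineligible patients may be enrolled. It lists "Failure to meet inclusion/exclusion criteria" as a violation and leaves to the sponsor whether the subject is withdrawn.

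SAP 4.3 lists adverse events as a safety outcome. SAP 5.1 defines one population, ITT, consisting of everyone randomized, and calls it primary. No safety population appears in the SAP.

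**The concern.** A safety set should count patients by exposure. Whether a patient should have been enrolled has no bearing on whether an ointment harmed them. An eligibility condition removes exposed patients, and in this trial the condition can be decided after allocation is known to everyone.

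That leaves two risks. Adverse events in treated patients could go uncounted. The exclusions could also differ between arms. For example, a surgeon who knows that a patient is assigned to the non-antibiotic ointment might be readier to give IV antibiotics during surgery, and that would make the patient ineligible. The documents give no evidence that this happened, but nothing in the definition prevents it from affecting the safety comparison.

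The wording on study drug is a lesser matter. An analyst programming from 13.1 alone could not tell with certainty which arm or arms the dose condition covers.

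**Working it through.** The plan states no figure for this point, so the check compares the texts.

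**1. Can a properly randomized patient become ineligible and still be treated?**
- Protocol 7.1 and 8 place randomization at recruitment, at the pre-operative visit. Protocol 9.1 lists randomization as step 5 and assignment of the surgery date as step 7.
- Protocol 5.3 excludes patients with oral or IV antibiotic use in the 10 days before the procedure. Visit 1 records recent antibiotic use, but the 10-day window closes only at surgery, which has no date when the patient is randomized.
- Protocol 5.3 also excludes patients who need IV antibiotics during the procedure. That is settled only in surgery.
- Protocol 12 leaves withdrawal of violators to a case-by-case decision, so such a patient may stay in and use the ointment.

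The answer is yes. A patient can be randomized correctly, meet an exclusion criterion later, apply the ointment, and fall outside the safety set as worded.

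**2. Is the eligibility judgement protected from knowledge of allocation?** No. Protocol 7.2 states that neither subjects nor investigators are blinded, and no section says when, by whom or on what information eligibility is settled for the analysis.

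**3. What does study drug mean?**
- Contrasted with placebo: Protocol 3.1, "Subjects will be randomly assigned to a study drug or to a placebo"; Protocol 7.4.2, "Study drug or placebo will be dispensed by an outpatient pharmacist"; and the first sentence of 13.1.
- Covering either ointment: Protocol 7.7, which applies to every subject, "Subjects will be asked to keep a patient diary noting the day and date they take their study drug and any adverse events"; Protocol 11.1 on stopping study drug; Protocol 12 on non-compliance with the regimen; and 13.4, where events in both treatment groups are classed by relationship to study drug.

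Usage is mixed. Because 13.4 tabulates by group and 4.2 asks for rates on both products, both arms are intended.

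**4. Does the SAP settle the population?** Protocol 13 says the SAP will describe all analyses and carry any modifications. For the main analysis, SAP 5.1 replaces the completers set of 13.1 with ITT. For adverse events, the SAP names the outcome (4.3) but does not link it to a population, and Section 6 has no part specific to it beyond the general statement on counts and percentages. ITT also differs from a safety set: it includes randomized patients who never applied an ointment.

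**5. Scale.** The documents give no ineligibility rate. With 400 planned patients (Protocol 13.6), each percentage point found ineligible after treatment corresponds to 0.01 × 400 = 4 patients across both arms. This converts a rate into a count; it does not estimate how many there would be.

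**The case against.** The strongest reply is that the restriction has little effect. Protocol 3.1 makes eligibility the entry gate, so *eligible patients who are randomized* may simply describe those who passed it. No text says that patients are later reclassified and taken out of the safety counts. Event capture (8.1.5), serious-event documentation from consent onward (10.2.1) and the monitoring committee's updates (4.3, 10.3) carry no eligibility condition. The SAP's only population is ITT, which a reasonable analyst might also apply to adverse events.

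Much of this stands. Events would still be recorded, reported and seen by the committee, so the exposure is confined to the final tabulation. But reading *eligible* as the entry gate is only one possible reading, and it makes the word redundant. The SAP never says that ITT covers safety.

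A reader might also infer that the control arm is left out of the safety set, which would remove 200 of the 400 planned patients. The documents do not support this. The term covers both ointments in several sections, and the by-group tabulation in 13.4 needs both arms. It is a wording ambiguity.

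A reader might further infer that the rates of contact dermatitis and dehiscence are at risk. SAP 4.2 lists these as secondary outcomes, and SAP 6.2 compares them between groups. Their natural population is ITT, which has no eligibility or dose condition.

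**Conclusion.** The point holds as a minor defect of definition. As written, Protocol 13.1 would leave adverse events in treated patients later found ineligible out of the tabulation, and the trial's sequence makes such patients foreseeable. The ambiguity over study drug should be removed at the same time, on the understanding that both arms are already intended.

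The size is unknown, and any assumed percentage would have no anchor in the documents. The effect is limited to the general adverse-event tabulation. The primary outcome and the SAP's secondary outcomes are not affected.

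The conclusion rests on two assumptions: that *eligible* is applied as an analysis condition, and that 13.1 still governs adverse events because the SAP is silent on them. If the sponsor intends ITT for safety, the eligibility problem disappears, but the SAP needs to say so.

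**What to change.** Replace the safety sentence in Protocol 13.1, and add the same definition to SAP 5.1: the safety set is all randomized patients who applied at least one dose of either ointment, regardless of eligibility. State in the SAP that adverse events are tabulated in this set by treatment group.

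The cost is one sentence in each document, plus the line linking adverse events to the set. It needs no new data and no change to sample size or trial conduct. The SAP already describes randomization and outcome assessment in the past tense. If the protocol can no longer usefully be amended, the definition can be fixed in the SAP before the safety tables are produced. Failing that, the report should state which set was used and how many treated patients, by arm, were found ineligible.

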### 13.2 Demographic and Baseline Characteristics

Age

Gender  
Race  
Smoker (Y/N)

### 13.3 Analysis of Primary Endpoint

T-test or a linear regression model (with no covariates other than study arm).

